4.2.7.4 Secondary Efficacy Analysis – Sensitivity Analyses

Two sensitivity analyses will be conducted for secondary efficacy endpoint #1:

- (i) Analysis as described for secondary endpoint #1 using PPS
- (ii) Analysis as described above but with full imputation of bicarbonate using central laboratory measurements, as described in section 3.3.2, is conducted before the response is assumed to be missing. In addition, the ANCOVA model will include a binary variable to indicate if the dependent variable is central laboratory measurement.

Two sensitivity analyses will be conducted for each of the secondary efficacy endpoints #2-#7.

- Principal secondary analysis as described where the logistic regression model will include: race, gender, age at baseline (<65, ≥65), CKD stage at baseline (3, 4), diabetes status at baseline (Yes, No), POCT bicarbonate level at entry (16-18, 19-20), POCT type (i-Stat, Piccolo) and baseline use of RAASi therapy (Yes, No) as independent factors.
- Principal secondary analysis as described but conducted in the PPS.

Due to the early termination of the trial, the sensitivity analyses described above will not be conducted due to an insufficient sample size.

Statistical Analysis Plan D9480C00022 - External 4.0

4.2.8 Safety

4.2.8.1 Adverse Events

An overall summary table of the number of subjects experiencing each category of AEs will be produced using the SSO and SSR. Analyses using the SSO will be restricted to AEs which occurred during the open-label correction period and will be presented overall. Analyses using the SSR will include AEs which occurred during the randomized placebo-controlled period and will be presented by treatment group received during the randomized placebo-controlled period and overall.

Any AE occurring within the defined 7-day follow-up period after discontinuation of IP will be included in the AE summaries. Treatment emergent adverse events (TEAEs) occurring prior to first dose of IP (i.e. before study day 1) which subsequently worsen in severity following dosing will be presented in the summary tables.

An overview table will summarize the number and percentage of subjects with at least one of the following AEs, where patients with more than one AE in a particular category are counted only once in that category, as well as the absolute counts of number of AEs. For the overall summary of subjects with any AEs, in the safety set randomized analysis group, the event rate will be displayed. This will be calculated as the Number of subjects with AEs divided by the total number of days at risk for AEs across all subjects in given group, multiplied by 365.25 multiplied by 100.

- Any AEs
- · Any AEs assessed by investigator as possibly related to treatment
- Any AEs with outcome of death
- Any SAEs (including events with outcome of death)
- Any SAEs leading to treatment discontinuation
- Any AEs leading to treatment discontinuation
- Any AEs leading to dose reduction of study treatment
- Any AEs leading to dose interruption of study treatment

• Any AEs leading to study discontinuation

The number and percentage of subjects reporting each AE will be summarized by system organ class (SOC) and preferred term (PT). Tables will be sorted by international order for SOC and PTs will be sorted alphabetically. The following summaries will be produced using the SSO and SSR:

- AEs by SOC and PT;
- Most common AEs (>5% in any treatment group) by SOC and PT;
- AEs assessed by investigator as possibly related to treatment, by SOC and PT;
- AEs by relationship to treatment, by SOC and PT;
- AEs by maximum intensity, by SOC and PT;
- AEs assessed by investigator as possibly related to treatment, by maximum intensity, SOC and PT;
- AEs leading to treatment discontinuation, by SOC and PT;
- AEs assessed by investigator as possibly related to treatment leading to treatment discontinuation, by SOC and PT;
- SAEs, by SOC and PT;
- SAEs related to treatment, by SOC and PT;
- AEs leading to death, by SOC and PT;

All AE data will be listed appropriately for all subjects including information on AE duration, intensity, seriousness, action taken, outcome, relationship as assessed by investigator, timing of onset of AE in relation to the first dose of study treatment in the open-label correction period, study treatment at the time of event.

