2.3 Analysis Periods

Analysis periods defined in this section are distinct from those used to describe the study design in the CSP and section 1.2 of the SAP.

Screening Period

The screening period is defined as the period from informed consent to the first dose of openlabel study or screen failure.

Open-label correction period

The open-label correction period refers to the period from first dose of open-label study treatment to the earliest date of randomization, withdrawal of consent, last contact with the subject or death.

Randomized placebo-controlled period

The randomized placebo-controlled period refers to the period from randomization to the earliest date of rescue treatment for hyperkalemia or low serum bicarbonate, last assessment during follow-up (day 36 ± 3), withdrawal of consent, last contact with the subject, or death.

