3.4.2 Adverse Events

Adverse events (AEs) and Serious adverse events (SAEs) will be collected from start of the open-label correction phase, throughout the treatment period and including during the follow-up period. In addition, SAEs will be recorded from the time of signing the informed consent form and will continue throughout the clinical study until the end of any follow-up prior; this applies even if the subject has not received any study treatment (as per the SOP: Reporting of Individual Safety Events in Clinical Studies). SAEs which occur after the end of the clinical study but with a suspected causal relationship to the IP will be reported by the investigator but will not be included in summary tables and listings.

A treatment emergent AE (TEAE) will be defined as an AE with the start date on or after the first dose date and up to (and including) 7 days after the last dose date or an AE which starts prior to first dose of IP (i.e. before study day 1) which subsequently worsen in severity on or after the date of first dose of IP and up to and including 7 days following the date of last dose of study medication. AEs which occur more than 7 days after the last dose date will only be listed. Similarly, the number of patients experiencing SAEs, AEs that led to withdrawal, AEs that led to death and treatment related AEs, and number of such events, will be summarized by treatment group.

AEs will be further categorized as either occurring during the open-label period, if the start date is on or after the first dose date during the open-label correction period and prior to the date of the first dose of treatment during the randomized placebo-controlled period, or occurring during the randomized placebo-controlled period if the start date is on or after the date of the first dose of treatment during the randomized placebo-controlled period.

The Medical Dictionary for Regulatory Activities (MedDRA) (using the latest or current MedDRA version) will be used to classify AEs system organ class (SOC) and preferred term (PT).

If the relationship to treatment is missing, then the AE will be considered as possibly related to treatment.

Other significant adverse events

An overview of edema-related events (grouped terms include preferred terms of edema, edema peripheral, generalized edema, fluid overload, fluid retention, hypervolemia, localized edema, and peripheral swelling)and instances of sK+ <3.5 will be presented.

Deaths

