4.2 Analysis methods

4.2.1 Subject Disposition and Analysis Sets Analyzed

Subject disposition will be listed and summarized by treatment group and overall. The number and percentage of subjects in the following categories will be summarized for subjects in the screened set:

- Screened;
- Did not enter open-label period (Screening failures) and associated reasons;
- Entered the open-label period and received treatment
- Entered the open-label period and did not receive treatment and associated reasons
- Randomized;
- Not randomized (Open-label period failure) and associated reasons;
- Randomized and received treatment;
- Randomized, did not receive treatment and associated reasons;
- Completed the study;
- Discontinued treatment and associated reasons (including use of rescue treatment);
- Terminated study and associated reasons;

The denominator used for percentages will be calculated as follows. The denominator for subjects who are screened or who did not enter the open-label period (and associated reasons) will be calculated using the number of screened subjects. The denominator for subjects who entered the open-label period and received treatment, who entered the open-label period and did not receive treatment (and associated reasons), randomized and not randomized (and associated reasons) will be calculated using the number of subjects who entered the open-label period. The remaining subject disposition categories will use the number of subjects who were randomized for the denominator. Categories will still be presented if 0 subjects satisfy the criteria.

The number of subjects in each of the analysis sets and the reasons for exclusion from each will be summarized for all screened subjects by treatment group and overall.

4.2.2 **Protocol Deviations**

All important protocol deviations (Section 2.2) leading to exclusion from the PPS will be listed and summarized by treatment group and overall for the FAS. Important protocol deviations will be further classified as either pandemic-related or excluding pandemic related important protocol deviations and will be summarized by treatment group and overall for the FAS.

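### Two closing rules for the randomized-phase adverse-event tables, one at first rescue and one not, with nothing to say which governs

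*SAP*

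**What the plan says.** Four places in the SAP bear on which AEs enter the by-arm tables for the Safety Set Randomized (SSR).

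- **Section 2.3** defines the period by name: "The randomized placebo-controlled period refers to the period from randomization to the earliest date of rescue treatment for hyperkalemia or low serum bicarbonate", or the last follow-up assessment, withdrawal of consent, last contact or death if earlier. It presents these as the SAP's own analysis definitions: "Analysis periods defined in this section are distinct from those used to describe the study design in the CSP".
- **Section 3.4.2** has a rule written for AEs. An AE is classed as "occurring during the randomized placebo-controlled period if the start date is on or after the date of the first dose of treatment" in that period. No end at rescue is given. The treatment-emergent window runs to 7 days after last dose, and "AEs which occur more than 7 days after the last dose date will only be listed".
- **Section 4.2.8.1** restricts the tables by the named period ("Analyses using the SSR will include AEs which occurred during the randomized placebo-controlled period") and then adds: "Any AE occurring within the defined 7-day follow-up period after discontinuation of IP will be included in the AE summaries". That sentence makes no exception for rescue.
- **Section 4.2.1** lists, among the disposition categories, "Discontinued treatment and associated reasons (including use of rescue treatment").

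On the measure, section 4.2.8.1 gives numbers and percentages of subjects throughout. Section 4 takes percentages out of the analysis-set total unless otherwise stated. The exception is the overall any-AE summary, where "in the safety set randomized analysis group, the event rate will be displayed". That rate is subjects with AEs divided by total days at risk, times 365.25, times 100. Days at risk is not defined.

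**The concern.** One period name has two ends, and the harm tables are built on that name. The starts differ too: randomization in section 2.3, first randomized dose in section 3.4.2. A programmer who follows the section 2.3 definition drops every AE that starts after a rescue. One who follows section 3.4.2 keeps those within 7 days of last dose. Both can point to the text, and the counts will differ.

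The choice is not neutral between arms. The primary endpoint is normokalaemia without hyperkalaemia rescue, and the trial expects SZC to do better. If it does, closing at rescue removes more AE time from placebo than from SZC. Events that follow a rescue, including SAEs, would be the ones removed. The safety objective compares SZC with placebo, and most of the comparison is read from percentages that take no account of time at risk.

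**Working it through.** The plan states no figure on this point, so there is none to reproduce. The check has two parts.

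**1. The rules side by side, for a rescued patient**

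| AE starts | Section 2.3 | Sections 3.4.2 and 4.2.8.1 (7-day sentence) |
|---|---|---|
| After first randomized dose, before rescue | counted | counted |
| After rescue, within 7 days of last dose | not counted | counted |
| More than 7 days after last dose | not counted | listed only |

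The middle row is the conflict. How wide it is depends on when dosing stops. If it stops at rescue, the row covers 7 days. If dosing continues, the row runs to 7 days after the eventual last dose, and the section 3.4.2 window is not shortened at all.

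**2. How large the artefact could be**

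From the SAP: end of treatment at Day 29, follow-up at Day 36, randomization at Day 2 or 3. Taking Day 3, the full window is 36 − 3 = 33 days.

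Assumed, because the SAP gives no rescue or AE rates:
- the same constant AE hazard in both arms, with 30% risk over 33 days;
- rescue at Day 15 in 20% of placebo and 5% of SZC patients;
- for the section 3.4.2 reading only, dosing stops at rescue.

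Formulas, with f the fraction rescued and w the window of a rescued patient:
- hazard λ = −ln(0.70)/33 = 0.01081 per day;
- crude AE proportion = f(1 − e^(−λw)) + (1 − f)(0.30);
- mean window = f·w + (1 − f)·33;
- rate per 100 patient-years = proportion ÷ mean window × 36,525.

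*Closed at rescue*, w = 15 − 3 = 12 days, risk in a rescued patient 1 − e^(−0.1297) = 0.1216:
- placebo 0.20 × 0.1216 + 0.80 × 0.30 = 26.4%;
- SZC 0.05 × 0.1216 + 0.95 × 0.30 = 29.1%;
- gap 2.7 points with no true difference.

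*Closed at rescue + 7 days*, w = 19 days, risk 1 − e^(−0.2054) = 0.1856:
- placebo 0.20 × 0.1856 + 0.80 × 0.30 = 27.7%;
- SZC 0.05 × 0.1856 + 0.95 × 0.30 = 29.4%;
- gap 1.7 points.

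*Effect of the rate.* Mean windows are 28.80 v 31.95 days (closed at rescue) and 30.20 v 32.30 days (rescue + 7). With days at risk taken as window length, the rate is 335 v 333 per 100 patient-years in both cases, so it nearly removes the gap. It does so only if numerator and denominator use the same window. Counting events to rescue + 7 but days only to rescue gives 0.2771 ÷ 28.80 × 36,525 = 351 v 0.2943 ÷ 31.95 × 36,525 = 336.

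*Range.* Over rescue splits of 10% v 2%, 20% v 5%, 30% v 5% and 40% v 10%, rescue at Day 8, 15 or 22, and AE risk of 30% or 50%, the spurious gap is 0.9 to 12.0 points if closed at rescue. It is 0.4 to 8.3 points if closed at rescue + 7 days. If every patient had one common window to Day 36, the gap would be zero.

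**The case against.** The best reply is that section 3.4.2 contains the AE-specific rule, that section 4.2.8.1 echoes its wording, and that the 7-day sentence confirms it. On that view section 2.3 is a general definition that AE tables would not follow. This is a reasonable reading and may be the intended one. But section 2.3 is not limited to efficacy, its period name is the one used in section 4.2.8.1, and nothing ranks the two. The conflict stands, though it cannot be said that the tables will close at rescue.

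Other points against a stronger reading are sound:

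- A reader might infer that both rules shorten the placebo window. Under section 3.4.2 that is so only for patients whose dosing stops at rescue. Section 4.2.1 lists rescue as a reason for discontinuation, but does not say that every rescue ends treatment. The estimand lists for the primary endpoint and the bicarbonate endpoints treat rescue and discontinuation as separate events.
- A reader might infer that deaths are lost. Section 4.2.8.2 summarises deaths separately with no rescue cut-off, includes categories beyond 21 days after last dose, and lists all deaths. Only the death rows of the AE tables are exposed.
- A reader might infer that the arms are compared on crude percentages alone. The any-AE rate exists, and section 4.2.8.7 summarises exposure by arm.
- The bias would make placebo look safer and so overstate SZC harm, not hide it.
- No between-arm AE test is described. At the planned 68 per arm, the standard error of a difference near 30% is √(2 × 0.30 × 0.70 / 68) = 7.9 points, larger than the central gap, and the trial stopped early.

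These limit the size and certainty of the bias. They do not settle which events are counted.

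**Conclusion.** The point holds as an unresolved conflict between section 2.3 and section 3.4.2, with section 4.2.8.1 drawing on both. If section 2.3 is applied, AEs and SAEs after rescue leave the by-arm tables in a treatment-dependent way. Only the any-AE row has a time-at-risk rate to offset this, and its denominator is undefined. If section 3.4.2 is applied, the distortion is smaller and conditional on dosing stopping at rescue.

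The gaps of about 2.7 and 1.7 points rest wholly on assumed rescue and AE rates and a constant hazard. They show the direction and a plausible order of size, and are not an estimate for this trial. The correction is worth making because it prevents a wrong event count at almost no cost, not because a large bias has been shown.

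**What to change.** 1. In sections 2.3 and 4.2.8.1, state that rescue does not close the randomized period for AE tables, and that the section 3.4.2 window applies: first randomized dose to 7 days after last dose.
2. In section 4.2.8.1, define days at risk on that same window, and say whether counting stops at a subject's first event.
3. Show the time-at-risk rate beside the percentages for SAEs and the other key rows of the SSR overview table.

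A repeat overview table of all AEs to last study contact, regardless of rescue or stopping, is optional. It would bring in some off-drug events.

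The cost is a few sentences of SAP text and a few extra table columns. The changes rest on the AE and dosing dates that the existing derivations already use.

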4.2.8.2 Deaths

A summary of deaths will be provided with number and percentage of subjects categorized as:

- Number of subjects with any AE with outcome = death
- AEs related to disease under investigation and with AE outcome of death
- AEs with outcome of death only (AE start date falling > 21 days after last treatment dose)
- Deaths > 21 days after last treatment dose, unrelated to AE or disease under investigation
- Deaths > 21 days after last treatment dose, AE related to disease under investigation and with AE outcome of death

All deaths will be listed.

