1.2 Study design

This is a prospective, randomized, double-blind, placebo-controlled, parallel, multicenter, Phase IIIb study to investigate the safety and efficacy of SZC in patients with hyperkalemia and low bicarbonate (or metabolic acidosis).

The study will be conducted in the United States (US) at approximately 35 investigative sites.

This study consists of a short screening visit (Day 1), an open-label correction period (up to 48 hours), a 4-week randomized treatment period, and a follow-up period (7 days after the last administration of study medication). The total study treatment duration, consisting of open-label and randomized periods, will be 29 days.

Screening will be performed using potassium and bicarbonate value from a study-approved point-of-care test (POCT) to determine eligibility of consenting patients to enter the openlabel correction phase. Patients who meet the POCT eligibility criteria of serum potassium (sK+) between 5.1-5.9 mmol/L inclusive, AND serum bicarbonate between 16-20 mmol/L inclusive, will be enrolled into the open-label correction phase. All baseline parameters should be measured/collected prior to administration of the first dose of study drug in the open-label initial phase.

In the open-label initial phase, patients will receive open-label SZC orally at a dose of 10 g three times daily (TID) for up to 48 hours, depending on POCT potassium value.

Patients who achieve normokalemia (K+ between 3.5 and 5.0 mmol/L inclusive) within 24-48 hours will be randomized 1:1 into the double-blind randomized treatment phase to receive 10 g SZC or placebo once daily (QD) starting dose for the following 28 days. Patients who achieve normokalemia after 24 hours will be randomized and will not need to continue on 10 g SZC TID for another 24 hours.

Study treatment will end with the Day 29 visit, which will be followed by the end of study visit 7 days after the last administration of study medication.

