All AEs leading to death will be collected until the end of the study.

Laboratory Data

Deterioration as compared to baseline in protocol-mandated laboratory values will only be reported as AEs if they fulfil any of the SAE criteria, are the reason for discontinuation of treatment with the IP or are considered to be clinically relevant as judged by the investigator (which may include but not limited to consideration as to whether treatment or non-planned visits were required or other action was taken with the study treatment, e.g., dose adjustment or drug interruption).

Vital Signs Data

Deterioration as compared to baseline in protocol-mandated vital signs should therefore only be reported as AEs if they fulfil any of the SAE criteria, are the reason for discontinuation of treatment with the IP or are considered to be clinically relevant as judged by the investigator (which may include but not limited to consideration as to whether treatment or non-planned visits were required or other action was taken with the study treatment, eg, dose adjustment or drug interruption).

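### Three of the five death rows are cut at more than 21 days after last dose in a trial with 7-day follow-up; they are empty for completers, and deaths without a fatal AE can fall in no row.

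*SAP*

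**What the plan says.** SAP section 4.2.8.2 gives five categories for the death summary, numbered here in their printed order:

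1. "Number of subjects with any AE with outcome = death", with no time limit.
2. Fatal AEs related to the disease under investigation, with no time limit.
3. "AEs with outcome of death only (AE start date falling > 21 days after last treatment dose").
4. "Deaths > 21 days after last treatment dose, unrelated to AE or disease under investigation".
5. "Deaths > 21 days after last treatment dose, AE related to disease under investigation and with AE outcome of death".

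The section adds that every death is listed. It has no row for total deaths.

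The rest of the SAP works with 7 days. In section 1.2 treatment ends at the Day 29 visit, "which will be followed by the end of study visit 7 days after the last administration of study medication". Section 3.4.2 defines treatment-emergent AEs up to and including 7 days after last dose and says that "AEs which occur more than 7 days after the last dose date will only be listed". Section 4.2.8.1 takes AEs from the 7-day follow-up into the AE summaries. Sections 2.3 and 3.1 (Table 1) put the last follow-up assessment at Day 36 ± 3, that is Days 33 to 39. On fatal events section 3.4.2 says: "All AEs leading to death will be collected until the end of the study". It keeps SAEs that arise after the study has ended out of both tables and listings.

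**The concern.** The 21-day figure appears only in section 4.2.8.2 and does not fit the length of observation in this trial. This has three consequences.

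- More than half of the table's rows cannot receive a patient who completes treatment.
- The only row meant for deaths not attributed to an AE or to the disease is one of those three. Earlier deaths of that kind have no row.
- The SAP tells the programmer both to tabulate fatal AEs that start more than 21 days after last dose and to keep every AE beyond 7 days out of the summaries.

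At stake is the count of deaths by arm in the safety summary. The table has no total row, so the number of patients who died cannot be read from it with certainty. The trial was terminated early with a small sample, so one death missing from the count would be noticeable.

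**Working it through.** **Inputs.** Last dose for a completer: Days 28 to 30 (Visit 7 protocol window, Table 1). The wider Visit 7 analysis window is Days 26 to 32. End of follow-up: Day 36 nominal, Days 33 to 39 with the window (Table 1, section 2.3). Cut-off in the death table: more than 21 days, so 22 days or more in whole days.

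**The plan's own follow-up figure.** 36 − 29 = 7 days. This reproduces the 7 days in section 1.2.

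**Longest observation after last dose for a completer.** Latest end of follow-up minus earliest last dose:

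- Protocol window: 39 − 28 = 11 days.
- Last dose placed at the start of the analysis window: 39 − 26 = 13 days.

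Both are below 22.

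**First day on which a 21-day row could count a completer's death.** Last dose + 22: 28 + 22 = Day 50, 29 + 22 = Day 51, 30 + 22 = Day 52. The last study day is 39.

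**Patients who stop drug early.** Latest last dose that allows a gap of 22 days: 39 − 22 = Day 17, or 36 − 22 = Day 14 if the last visit is on Day 36. This requires observation up to the planned last visit. If such a patient instead has the end-of-study visit 7 days after last dose, as section 1.2 reads, the rows are empty for that patient too.

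**Which rows each kind of death meets.** Row 3 is read as fatal AEs not related to the disease, row 4 as deaths with neither a fatal AE nor a disease cause. AE onset and death are placed at the same distance from last dose.

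| Kind of death | 0 to 21 days after last dose | 22 days or more |
|---|---|---|
| Fatal AE, disease-related | rows 1, 2 | rows 1, 2, 5 |
| Fatal AE, not disease-related | row 1 | rows 1, 3 |
| No fatal AE, disease-related | none | none |
| No fatal AE, not disease-related | none | row 4 |

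For a completer only the middle column can occur, so a completer's death without a recorded fatal AE always has no row.

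**Conflict with section 3.4.2.** An AE that starts more than 21 days after last dose also starts more than 7 days after it. Section 3.4.2 sends it to the listing only; row 3 counts it in a table. Nothing in section 4.2.8.2 declares an exception.

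**The case against.** The best defence is that little is lost. Row 1 has no time limit and takes in every fatal AE. Fatal AEs also appear in the overview and in the tables by system organ class and preferred term (section 4.2.8.1). All deaths are listed. Section 4.2.1 summarises reasons for study termination by treatment group, so an in-study death may be counted there, although the reason categories are not given. An empty row in a descriptive table misstates nothing by itself, and the SAP gives no expected number of deaths without a fatal AE. All of this stands and limits the point to tabulation; deaths are still captured.

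Three stronger readings are tempting and should not be drawn.

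- A reader might infer that the split was meant to separate on-treatment from post-treatment deaths and fails at it. The SAP states no such purpose.
- A reader might infer that a death 8 to 21 days after last dose is classified in two contradictory ways. Section 3.4.2 goes by AE start date, whereas rows 4 and 5 go by date of death. An AE that starts on day 5 and is fatal on day 12 is treatment-emergent and sits in row 1, without contradiction. Only row 3 uses AE onset, and there the conflict is with the listing-only rule.
- A reader might infer that the 21-day rows can never be used. The primary estimand (section 4.2.7.1) handles treatment discontinuation by treatment policy, and section 2.3 runs the period to Day 36 ± 3, so an early stopper may still be observed late enough.

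It is also fair to say that merely replacing 21 by 7 would be a poor remedy. Completers have nominally 7 and at most 11 days of observation, so rows beyond 7 days would fill only through visit-window slack. The rows would still overlap, and a disease-related death without a fatal AE would still have none.

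**Conclusion.** The point holds, with minor severity. The 21-day rows are structurally empty for completers: at most 11 days are observed (13 on the widest reading of the visit windows) against the 22 needed. Deaths without a fatal AE have no row within 21 days of last dose, and when disease-related they have none at any time. Row 3 contradicts the listing-only rule in section 3.4.2. The table can therefore undercount deaths by arm.

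This rests on two assumptions: that observation ends with the Visit 8 window on Day 39, and that a death can be recorded without an AE of fatal outcome. Row 4 itself presupposes the second. The effect stays within one descriptive safety table; efficacy inference, type I error and sample size are untouched.

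**What to change.** In SAP section 4.2.8.2:

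- Add a row for total deaths from any cause by treatment group, split into deaths up to 7 days and deaths more than 7 days after last dose, whether or not a fatal AE was recorded. Each death is then counted once in that row.
- In the three rows that use 21 days, substitute the same 7-day window, or drop those rows. With the total row in place, dropping them loses little.
- State that fatal AEs starting after the 7-day window are counted in this table as an exception to the listing-only rule in section 3.4.2.

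The cost is a wording change and one table-shell edit. No new data are needed.
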